9.1.9. Procedure Related Adverse Events

Adverse events with an onset date within 7 days of the insert procedure will be clinically reviewed to assess the relationship to the injection procedure. Events that could be considered related to the injection procedure could include but is not limited to events such as decreased IOP, increased IOP, eye pain, eye erythema, etc. The process by which the manual review is conducted will be summarized in a manual data review memo. Events which are deemed related to the injection will be summarized in similar manner as incidence of adverse events detailed in section 9.1.1.

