7.5. Measures Taken to Minimize Bias

At least 10 different investigators will administer the FAI insert, and randomization will be stratified by investigator.

Each time a subject's eye is enrolled in the study, one investigator will serve as the treating investigator (Investigator); another person will serve as the trained observer (Observer). On study Day 1, the Investigator will administer the FAI insert, and the Observer will observe the procedure used by the Investigator to administer the FAI insert. The Investigator and the Observer will complete questionnaires related to the administration of the FAI insert on Day 1. The Investigator (or designee) will perform all subsequent study assessments. Study personnel will not disclose to the subject which inserter was used for intravitreal administration of the FAI insert.

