3.2. Study Endpoints

The primary utilization and safety analyses of the inserters will be conducted at Day 7; safety analyses of the FAI insert will be conducted at Day 7 and Month 12. Analyses will be based on individual eyes.

Evaluation of Mk II inserter and Mk I inserter

Utilization evaluation (based on individual eye):

The primary utilization endpoint is defined as the proportion of intravitreal insertion procedures that are assessed by the Investigator as satisfactory. A satisfactory procedure is defined as one receiving a score from the Investigator as either Very Easy (VE), Easy (E), or Routine (R), according to the following categories:

- Very Easy (VE)
- Easy (E)
- Routine (R)
- Difficult (D)
- Very Difficult (VD)

Secondary utilization endpoints include:

- Clarity of the Instructions for Use, as assessed by the Investigator
- Differences between observed procedure and instructions for use, as assessed by an Observer

Safety evaluation (based on individual eye):

Safety will be evaluated over one period: Day 1- Day 7, and will include:

• Ocular adverse events, including: procedure-related adverse events, IOP increase/decrease, medications/procedures required to treat adverse events, clinically significant ocular changes

Evaluation of the FAI insert

Safety will be evaluated for two periods: through Day 7 and through Month 12. Descriptive statistics will be used to present the results of all safety evaluations and will include:

- Ocular adverse events (base on individual eye), including: IOP increase/decrease, medications/procedures required to control elevated/low IOP, development or worsening of cataract, cataract-related procedures, clinically significant ocular changes
- Systemic adverse events

4. General Statistical Considerations

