Continuous data will be described using descriptive statistics (i.e. n, mean, standard deviation, median, minimum, and maximum). Categorical data will be described using the eye/subject count and percentage in each category. For the summary statistics of all numerical variables unless otherwise specified, minimum and maximum will be displayed to the same level of precision as reported. Mean and median will be displayed to one level of precision greater than the data collected. Standard deviation / standard error will be displayed to two levels of precision greater than the data collected. P-values will be rounded to three decimal places. If a p-value is less than 0.001 it will be reported as "<0.001". If a p-value is greater than 0.999 it will be reported as ">0.999".

Data will be displayed in all listings sorted by treatment group, unless otherwise specified. A subject will be assigned by the study site. The first 3 digits of the ID number will be the assigned site number, followed by a 3-digit subject number in sequential order (i.e., 201001, etc.). Within the IWRS system, at the time of randomization, a 1-digit eye identification number will be added: the subject's first eye (if eligible) to be randomized will be assigned the additional digit "1" (e.g., 201001-1); the subject's second eye (if eligible) to be randomized will be assigned the additional digit "2" (e.g., 201001-2). However all data within the clinical data base will be recorded based on the subject number (without the eye id) and eye level data will be recorded as OD or OS. For non-ocular/systemic assessments, subjects who have more than one eye randomized/treated will have data listed once for each different treatment received. (e.g., the data could be listed for both the Mk II and Mk I injectors.)

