4.3. Masking of Study Subjects

Treatment assignments will be masked to study subjects. Any non-study eye may receive any standard treatment at the discretion of the Investigator.

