9.1.8. Adverse Events of Special Interest

A summary of TEAEs of cataract and elevated IOP will be presented in a table by treatment group and all treated eyes. These TEAEs will be also summarized for subject level. Events will be included in the summary based on a list of PTs for each event category. Cataract events will include any event whose MedDRA higher lever coded term is "CATARACT CONDITIONS" is contained in the preferred term. IOP elevations will be based on the specific preferred term "INTRAOCULAR PRESSURE INCREASED" or if the preferred term contains the phrase "GLAUCOMA".

A summary of ocular TEAEs which are considered complications of IOP lowering medications to control IOP will be presented by treatment group and all treated eyes. These TEAEs will be also summarized for subject level. Events will be included in the summary based on manual review of AEs with an onset date on or after the date of first use of any IOP lowering medication.

A summary of ocular TEAEs which are considered complications of surgical interventions to control IOP will be presented by treatment group and all treated eyes. These TEAEs will be also summarized for subject level. Events will be included in the summary based on manual review of all AEs with an onset date on or after the date of surgical intervention. A similar summary will be presented for complications of cataract surgeries.

At each level of eye summarization, an eye is counted once for multiple events within PT. Percentages will be calculated out of the number of eyes in the Safety population. At each level of subject summarization, a subject is counted once for multiple events within PT. Percentages will be calculated out of the number of subjects in the Safety population. The summary will be sorted by PT in alphabetical order. Adverse events of special interest will be summarized at Day 7 and Month 12.

A manual data review memo will be written at the time the manual data reviews are performed. Because investigators may report similar events differently, the memo will be written a the time of the manual review to document the specific details on the preferred terms and other text specifications that are used to identify IOP lowering medications, IOP surgeries, and Cataract surgeries.

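### SAP 9.1.9 identifies procedure-related adverse events by a clinical review with open-ended criteria and no requirement that the reviewer be masked to inserter

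*SAP*

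**What the plan says.** The primary objective (SAP 2.1, Protocol 6.1) covers safety of the Mk II inserter through 7 days. SAP 3.2 lists the content of that evaluation: "Ocular adverse events, including: procedure-related adverse events, IOP increase/decrease", followed by treatments needed for adverse events and clinically significant ocular changes.

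SAP 9.1.9 sets out how procedure-related events are identified. Events with onset within 7 days of the procedure "will be clinically reviewed to assess the relationship to the injection procedure". The guidance on what counts is illustrative: "Events that could be considered related to the injection procedure could include but is not limited to events such as decreased IOP, increased IOP", then eye pain, redness and an open-ended close. On documentation: "The process by which the manual review is conducted will be summarized in a manual data review memo". The section does not say who reviews, what material the reviewer receives, or whether the inserter is concealed.

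Three other statements bear on this:

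- **Masking (SAP 4.3):** "Treatment assignments will be masked to study subjects". No other party is masked.
- **Listings (SAP Section 4):** "Data will be displayed in all listings sorted by treatment group, unless otherwise specified". SAP 9.1.9 does not specify otherwise.
- **Follow-up (Protocol 7.5):** "The Investigator (or designee) will perform all subsequent study assessments". This is the person who used the inserter, or a delegate.

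**The concern.** Whether early eye pain, redness or a pressure change was caused by the injection is a judgement, and many of these calls will be borderline. If the person judging knows which inserter was used, the threshold can differ between arms without anyone intending it. The result is differential misclassification, which can create or hide a difference between inserters.

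This table matters because no other planned adverse event table isolates the procedure. Protocol 11.2.1 has the Investigator give one causality rating covering product, device or procedure together, and SAP 9.1.2 tabulates it as a single relationship to study treatment. Only the serious adverse event report (Protocol 11.4.1) asks for causality to medication, device and procedure. A reader who wants to know whether one inserter causes more procedural events will look at the 9.1.9 table.

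**Working it through.** **1. The plan's own figures.** The documents give no expected rate of procedure-related events. The only sample-size figures are the widest exact 95% intervals for the satisfactory-procedure proportion (SAP 4.1). The Clopper-Pearson limits are the 0.025 quantile of Beta(x, n − x + 1) and the 0.975 quantile of Beta(x + 1, n − x).

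- 10/20: 27.2% to 72.8%, as stated.
- 5/10: 18.7% to 81.3%, as stated.

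The planned arm sizes of 20 and 10 eyes are used below.

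**2. Weight of one decision.**

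- Mk II: 1/20 = 5 percentage points.
- Mk I: 1/10 = 10 percentage points.

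**3. Size of a spurious difference, under assumptions.** Let both arms have the same true rate p of procedure-related events, and let the review keep a fraction s of them in each arm. The expected difference, Mk II minus Mk I, is p × (s_II − s_I). The values of p and s are assumed, because the documents give none.

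| Kept, Mk II / Mk I | p = 20% | p = 30% | p = 40% | p = 50% |
|---|---|---|---|---|
| 100% / 100% | 0 | 0 | 0 | 0 |
| 80% / 100% | −4 | −6 | −8 | −10 |
| 60% / 100% | −8 | −12 | −16 | −20 |

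Entries are percentage points. For example, 0.40 × (0.80 − 1.00) = −0.08. Reversing the two fractions reverses the sign.

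**4. In whole eyes.** Start from 8/20 and 4/10, both 40%.

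- Two Mk II eyes no longer counted: 6/20 = 30% against 40%, Fisher p = 0.69.
- Four Mk II eyes no longer counted: 4/20 = 20% against 40%, Fisher p = 0.38.

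The exact 95% interval for 4/10 is 12.2% to 73.8%, so these shifts lie well inside sampling error. They would still change the descriptive percentages, which are what the plan reports.

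**5. Whether existing tables show the effect of the review.** SAP 9.1.1 tabulates all ocular treatment-emergent events by inserter without any review. However, the Day 7 analysis takes data to study day 10 (SAP Section 4), while 9.1.9 takes onsets within 7 days. No planned table shows the 9.1.9 candidate set before review, so a reader cannot see how many events the review removed in each arm.

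**The case against.** The strongest reply is that the SAP is silent rather than wrong. SAP 9.1.9 does not say that the reviewer sees the inserter, and its memo could describe a masked process. The sorting rule governs how listings are displayed and does not say that they are the reviewer's worksheet. This is correct. A reader might infer that the plan has the review done with the inserter visible, but the documents show only that nothing prevents it.

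Three other tempting readings go too far.

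- **Criteria written only at the review.** SAP 9.1.8 says "A manual data review memo will be written at the time the manual data reviews are performed". That paragraph is about terms identifying IOP-lowering medications, IOP surgeries and cataract surgeries. SAP 9.1.9 gives its own memo no date. What stands is that 9.1.9 sets no criteria in advance.
- **The main safety comparison.** Procedure-related events are one item among several. All ocular events (SAP 9.1.1), the protocol-defined ocular events summarised there, and measured IOP including the Day 1 post-administration value (SAP 9.2.2) are reported by inserter without this review.
- **A sponsor expectation that Mk II is safer.** SAP Section 1 and Protocol 5.3 expect it to be easier to use. They do not predict fewer adverse events.

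It is also fair to say that no decision rests on the table. Safety is descriptive (SAP Section 9), success depends on the ease-of-use score (SAP 8.1.1), and the study is not powered for an inserter difference even on that endpoint (SAP 4.1). These points limit the importance of the concern. They do not answer it, because the other adverse event tables mix procedural events with drug and disease events.

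**Conclusion.** The concern holds as a gap in the plan. A judgement-based classification feeds one named component of the Day 1 to Day 7 inserter safety evaluation. It has no fixed criteria and no required masking, in a trial where only subjects are masked. The by-inserter comparison in that table is open to differential classification, at 5 points per Mk II eye and 10 points per Mk I eye if enrolment is 20 and 10.

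The larger shifts of 4 to 20 points rest on assumed event rates and assumed differences in classification. They illustrate sensitivity and do not forecast bias. The documents do not establish that the reviewer will be unmasked or that the calls would favour either inserter. The trial's success conclusion is unaffected. This is a cheap improvement worth making before the Day 7 analysis.

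**What to change.** Amend SAP 9.1.9 to state that:

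1. the candidate terms and relatedness criteria are fixed before the review begins;
2. the review uses a listing with inserter, randomization and device-identifying text removed, sorted by a neutral key;
3. the decisions are locked before treatment is merged;
4. all ocular treatment-emergent events with onset within 7 days are tabulated by inserter beside the reviewed subset.

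Masking loses nothing the reviewer needs: the question is relatedness to the injection, and both arms receive one. Item 4 makes the effect of the review visible whatever it finds. The change can stay within 9.1.9. The manual reviews in 9.1.8 concern complications of IOP treatment and cataract surgery, and this argument does not extend to them.

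The cost is SAP wording, one extra listing, one extra table, and redaction of free text that identifies the device. Sample size and visits do not change. The fix does not remove bias that enters earlier, when an Investigator who knows the inserter reports the events.

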9.1.10 Other Meaningful Adverse Events

Ocular events which occur in non-treated eyes and ocular events which occur in the second treated eye with a start date on or after the date of treatment in the first study eye but before the date of treatment in the second eye will be summarized by SOC and PT. At each level of summarization, an eye is counted once for multiple events within PT/SOC. Summaries will be for total eyes and not by randomized treatment group(s) for the first/second eye. Percentages will be based on the number of non-treated eyes or the number of second treated eyes, respectively. A similar summary of serious adverse events will also be provided. Ocular events in non-treated eyes will be presented. Events in the second study eye prior to date of treatment in the second treated eye.

9.2. Ophthalmic Examination

All ophthalmic examinations are performed on both eyes.

9.2.1. Best-corrected Visual Acuity (BCVA)

BCVA will be measured according to the standard procedure developed for ETDRS at 4 meters (or at 3 meters if the electronic ETDRS system is employed). Corrected-distance VA is to be reported as number of letters read correctly by the subject. The Snellen Fraction will also be recorded. If the subject is unable to read any letters at 4 meters or 1 meter, the investigator will assess the subject's ability to count fingers, recognize hand motion, or light perception.

A summary table presenting the observed values and changes from baseline in BCVA (letters) will be presented by treatment group for the Safety population. Changes from baseline to each scheduled post-baseline visit will be presented. In addition, a categorical summary of change from baseline in BCVA will present the letter change at Day 7 (or Month 12) and the maximum letter change at any time point up to Day 7 (or Month 12), including categories of \geq 15 letters lost, \geq 10 letters lost, \geq 5 letters lost, no change, \geq 5 letters gained, \geq 10 letters gained, and \geq 15 letters gained.

The BCVA summaries will also be presented for the following subgroups:

- IOP lowering medication [No IOP lowering medication, Required IOP lowering medication]
- Surgical Intervention to Control Elevated IOP [No surgical intervention, Required surgical intervention]
- Lens status at Baseline [Phakic, Aphakic, Pseudophakic]

IOP lowering medication status will be based on a subject's use of any IOP lowering medication up to the time point of interest (Day 7 and Month 12). Surgical intervention status will be defined in a similar manner.

For eyes with phakic lens status at study entry who undergo cataract surgery while in the study, the change in BCVA (letters) from the last BCVA measurement prior to surgery to the first BCVA measurement after surgery will be summarized by treatment group for the Safety population. In addition, a summary of change from baseline in BCVA (letters) will be presented by treatment group with phakic eyes at study entry who undergo cataract surgery while in the study vs. eyes with a lens status of pseudophakic at study entry.

BCVA data will be presented in a listing.

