8.2. Subject Exclusion Criteria

- 1. Allergy to fluocinolone acetonide or any component of the FAI insert
- 2. Ocular malignancy in either eye, including choroidal melanoma
- 3. Uveitis with infectious etiology
- 4. Current viral diseases of the cornea and conjunctiva including epithelial herpes simplex keratitis (dendritic keratitis), vaccinia, and varicella
- 5. Current mycobacterial infections of the eye or fungal diseases of ocular structures
- 6. Subjects who yield, during screening, a confirmed positive test for human immune deficiency virus (HIV) or syphilis
- 7. Systemic infection within 30 days prior to study Day 1
- 8. Peripheral retinal detachment in area of insertion
- 9. Elevated intraocular pressure (IOP) > 21 mmHg, or chronic hypotony < 6 mmHg
- 10. Concurrent therapy at Screening with IOP-lowering pharmacologic agent in the study eye
- 11. Current diagnosis of any form of glaucoma or ocular hypertension in study eye at Screening, unless study eye has been previously treated with an incisional surgery procedure that has resulted in stable IOP in the normal range (10-21 mmHg)
- 12. Known history of clinically significant IOP elevation in response to steroid treatment in either eye, unless study eye has been previously treated with an incisional surgery procedure that has resulted in stable IOP in the normal range (10-21 mmHg)
- 13. Ocular surgery or capsulotomy performed on the study eye within 30 days prior to study Day 1
- 14. Intravitreal treatment of study eye: with FAI insert within 36 months prior to study Day 1; with Retisert within 30 months prior to study Day 1; with Ozurdex within 90 days prior to study Day 1; or with Triesence or Trivaris within 30 days prior to study Day 1
- 15. Peri-ocular or subtenon steroid treatment of study eye within 30 days prior to study Day 1
- 16. Treatment with an investigational drug or device within 30 days prior to study Day 1, except the FAI insert within this protocol

- 17. Pregnant or nursing females; females of childbearing potential who are unwilling or unable to use an acceptable method of contraception as outlined in this protocol from at least 14 days prior to study Day 1 until the Month 12 Visit
- 18. Any condition which, in the judgment of the Investigator, could make the subject inappropriate for entry into this study

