7.1.2 Concomitant Medications

Concomitant medications are defined as those medications which are taken on or after the initiation of study treatment (Day 1). This includes medications which start prior to Day 1 but continue while the subject is on treatment.

Concomitant non-ocular medication will be summarized by treatment group for ATC level 1 term, ATC level 2 term and preferred term for the Safety population. The concomitant nonocular medication data will be also summarized for all subjects at the subject level. Summaries by treatment group will be based on the number of treated eyes; therefore a subject who has both eyes treated will be counted more than once, "repeating" and counting the non-ocular medication once for each treated eye. Percentages for the by treatment summaries will be based on the number of treated eyes and percentages for the total subjects summary will be based on the number of subjects who have at least one eye treated.

Concomitant ocular medication will be summarized by treatment group and for all treated eyes for each drug class and preferred term for the Safety population. Percentages will be based on the number of treated eyes.

An additional summary of concomitant medication for each of the specified reasons for medication (recurrence of uveitis, treatment emergent AE, increased IOP, cataract, other) will be reported as well.

7.1.3 **IOP Lowering Medications**

The number and percentage of eyes requiring IOP lowering medication to control elevated IOP will be summarized by treatment group and for all treated eyes. Any systemic medications will be summarized as received in both eyes. IOP lowering medications will be identified as those medications with a reason for medication of "Increased IOP". Incidence will be summarized through 12 months and for 3 month time intervals through 12 months.

The number of medications (one, two, \geq three) required to achieve adequate IOP control will also be included in the summary. IOP medications will be counted at the "ingredient" level. For example, if the subject is receiving COSOPT (which contains two ingredients TIMOLOL MALEATE and DORZOLAMIDE HYDROCHLORIDE) and TIMOLOL MALEATE at the same time, the subject will be included in analysis as receiving two medications.

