A single medication must be used for a minimum of 7 days. Multiple medications must be used concurrently for a minimum of 14 days. A subject does not need to be taking the same medication(s) over a given period to be counted for analysis. For example, if a subject is taking Medication A from days 50 to day 55, then Medication B from days 56 to 62, the patient will be counted as receiving 1 medication to control IOP, because the subject required at least one IOP medication/ingredient for 7 consecutive days, even though each medication/ingredient was used for less than 7 days. In a similar example, if a subject was receiving Medication A from days 50 to 60, Medication B on days 61 to 70, and Medication C on Days 52 to 70, then the subject will be counted in the analysis as receiving 2 medications, because the subject received two unique medications/ingredients over days 52 to 70.

Because medications can start and stop at various times in the analysis periods (up to month 3, month 3 to month 6, etc.) a medication will be counted in a given period if the start date(s) for the required number days of consecutive use (7 days for a single medication, 14 days for multiple medications) occurs within the period, even if the end of the 7 or 14 days of consecutive use falls after the end of the given analysis period. Medication(s) which begin in one analysis period and continue to the "next" analysis period will be counted in the "next" analysis period only if the medication(s) were received for at least 7 or 14 days (for single or multiple medications, respectively) in the "next" period.

A summary of IOP lowering medications will also be presented by history of incisional surgery to control elevated IOP (History of Incisional Surgery, No History of Incisional Surgery). All summaries will be performed using the Safety population for the final analysis at Month 12 only.

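### SAP 9.2.1 sets the IOP-treatment subgroups for BCVA by subject rather than by eye, so fellow-eye treatment can label an untreated study eye as having required it (minor)

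*SAP*

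**What the plan says.** SAP 3.2 sets the unit of analysis: "Analyses will be based on individual eyes". SAP 9.2.1 then presents BCVA in subgroups, the first being "IOP lowering medication [No IOP lowering medication, Required IOP lowering medication", with a matching pair for surgery to control IOP. Membership is fixed by one sentence, "IOP lowering medication status will be based on a subject's use of any IOP lowering medication up to the time point of interest", followed by "Surgical intervention status will be defined in a similar manner".

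Two other sections count the same treatments by eye:
- SAP 7.1.3: "The number and percentage of eyes requiring IOP lowering medication to control elevated IOP will be summarized by treatment group and for all treated eyes". It identifies these drugs by a recorded reason of increased IOP and sets a duration rule, "A single medication must be used for a minimum of 7 days" (14 days for concurrent drugs). For drugs that are not local it adds: "Any systemic medications will be summarized as received in both eyes".
- SAP 7.2.1 counts eyes that needed surgery to control IOP, and its listing gives the eye operated on and the study-eye designation.

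Eligibility leaves room for a treated fellow eye. Exclusion 10 in Protocol 8.2 reads "Concurrent therapy at Screening with IOP-lowering pharmacologic agent in the study eye", and exclusion 11 (glaucoma or ocular hypertension) is also limited to the study eye. Protocol 9.7.1 and SAP 4.3 leave treatment of a non-study eye to the investigator.

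**The concern.** The subgroups are there to show vision in eyes that did, and did not, need IOP treatment after the insert. With status taken from the subject, a study eye with normal pressure and no treatment joins the Required group because its fellow eye was on drops, possibly since before the study. In a subject with two study eyes, treatment of one labels both, even where the two received different inserters. The Required group is then diluted with eyes that never had the problem. The same eye can also count as unmedicated in the 7.1.3 table and as Required in the 9.2.1 table of the same report.

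**Working it through.** **1. The rules side by side**

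| SAP section | Unit | Reason for treatment | Duration | Start of period |
|---|---|---|---|---|
| 7.1.3, local drugs | eye | increased IOP | 7 or 14 days | within the analysis periods to Month 12 |
| 7.1.3, systemic drugs | both eyes | increased IOP | 7 or 14 days | same |
| 7.2.1, surgery | eye | increased IOP, plus review of surgeries recorded as other | none | overall and 6-month intervals |
| 9.2.1, BCVA subgroups | subject | not stated | not stated | not stated; only an upper limit |

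**2. Can the case arise, and would the data show it?** A subject whose non-study eye is on drops is not barred by exclusion 10 or 11. Protocol 9.14 puts all concomitant medications on the eCRF, so fellow-eye drops would be in the data. Surgery is less certain: SAP 7.2 says all ocular surgeries are recorded, while Protocol 9.9 limits non-study-eye eCRF entry to adverse events. That doubt does not apply to subjects with two study eyes.

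**3. How many eyes are exposed?** Both documents plan about 25 subjects and 30 eyes. So 30 − 25 = 5 subjects have two study eyes, and 25 − 5 = 20 have one study eye and an untreated fellow eye. Every study eye with a fellow eye is exposed to the rule.

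**4. Size.** The plan gives no figure on this point. Its only design figures, the exact intervals of 27.2% to 72.8% (10/20) and 18.7% to 81.3% (5/10), reproduce and do not bear on it. Let p be the share of study eyes truly treated for IOP, and q the chance that the fellow eye was treated when the study eye was not. Neither is in the documents, so both are assumed.

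- Share labelled Required = p + (1 − p)q
- Falsely labelled part of that group = (1 − p)q / [p + (1 − p)q]

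| p | q | Labelled Required | False part of the group |
|---|---|---|---|
| 10% | 5% | 14.5% | 0.045/0.145 = 31% |
| 10% | 20% | 28% | 0.18/0.28 = 64% |
| 20% | 5% | 24% | 0.04/0.24 = 17% |
| 20% | 10% | 28% | 0.08/0.28 = 29% |
| 20% | 20% | 36% | 0.16/0.36 = 44% |
| 30% | 5% | 33.5% | 0.035/0.335 = 10% |
| 30% | 20% | 44% | 0.14/0.44 = 32% |

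The expected number of mislabelled eyes is 30(1 − p)q. It runs from 30 × 0.70 × 0.05 = 1.05 to 30 × 0.90 × 0.20 = 5.4. At p = 20% and q = 10%, 30 × 0.28 = 8.4 eyes are labelled Required, against 30 × 0.20 = 6 that should be.

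**The case against.** The best defence is that eye-level status is what the authors meant. SAP 7.1.3 also says subject in its worked examples, although its table counts eyes. The 9.2.1 labels echo the by-eye topics of 7.1.3 and 7.2.1, and the disputed sentence can be read as mainly fixing the time cut. The definition in 7.1.3 of an IOP-lowering drug by its recorded reason may also be meant to carry over. This makes a wording slip plausible, but 9.2.1 does not refer back to either section. A carried-over reason would not settle the matter either, since fellow-eye drops can have the same reason.

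The exposure is also narrower than exclusions 10 and 11 alone suggest. Exclusion 12 bars known steroid-related IOP elevation in either eye, unless the study eye has had successful incisional surgery, and exclusion 9 (IOP above 21 mmHg) names no eye. Both favour the lower values of q without removing the case.

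A reader might infer that fellow-eye disease is carried into the 12-month rate of eyes needing IOP treatment. The documents do not support this for local drugs or surgery, which are counted by eye. It can happen in 7.1.3 only through a systemic drug given for increased IOP and meeting the duration rule, whereas Protocol 9.12 describes pharmacologic treatment as eye drops. Nor is counting a systemic drug in both eyes an error: it reaches both eyes, and the rule is explicit and conservative for safety. Requiring a recorded elevation in the eye instead could miss true cases, because visits are sparse and non-study ophthalmologists may treat.

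**Conclusion.** The point holds for SAP 9.2.1 as written: both subgroup statuses follow the subject, against the by-eye unit in SAP 3.2 and the by-eye counts in 7.1.3 and 7.2.1. The medication limb is firm. The surgery limb is firm for subjects with two study eyes, and for the others depends on whether fellow-eye surgery reaches the eCRF.

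Under the assumed ranges, about 1 to 5 of 30 eyes would be mislabelled, forming 10% to 64% of the Required subgroup. These figures illustrate sensitivity; they do not estimate what will happen.

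Severity is minor. The effect is confined to descriptive BCVA subgroup tables in a study that SAP 4.1 says is not powered to detect a difference between inserters. It would go too far to infer a distorted inserter comparison or a distorted IOP safety rate: the primary endpoint, the success rule, IOP-surgery incidence and local-drug incidence do not use this status.

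**What to change.** In SAP 9.2.1, define both statuses by the study eye: IOP-lowering medication given to that eye, or IOP surgery performed on it, on or after its own injection and up to the time point. Refer to 7.1.3 for the reason and duration rules on drugs and to 7.2.1 for the identification of surgery, so that all three sections classify an eye alike.

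Keep the 7.1.3 rule for systemic drugs. At most, add a footnote giving the number of eyes counted only because of a systemic drug.

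The cost is a few lines of SAP text and a match by eye in the program; SAP section 4 already has eye-level data recorded as OD or OS. One detail needs a sentence. The 7.1.3 summaries are planned for Month 12 only, and the Day 7 analysis stops at study day 10. A drug started on day 5 and still in use then has 10 − 5 + 1 = 6 observed days, so the SAP should say how ongoing use counts against the 7-day minimum in the Day 7 subgroups.
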